**Projected Overall Study Timeline**

	Study Start-Up	Enrollment	Data Entry and Analysis	Study Write-Up
06/2016	X			
06/2016 – 07/2017		X		
07/2017 – 08/2017			X	
08/2017 – 09/2017				X

## 10.0 DRUG INFORMATION

**Drug Name:** Preservative-free isobaric bupivacaine 0.5%

**Other Names:** Marcaine 0.5%

**Classification:** Amide Local Anesthetic

**Mode of Action:** Blocks sodium influx into nerve cells by binding to voltage gated sodium channels

**Storage and Stability:**

**Metabolism:** Metabolized by the liver

**Preparation:** Mixed with glucose in sterile fashion

**Administration:** Administered intrathecally

**Incompatibilities:**

- Contraindications* – Allergy to amide local anesthetics
- Precautions* – Cardiotoxicity

### **Side Effects:**

Adverse effects indicated in *italics* are the most frequent adverse effects.

Adverse events in **bold** are severe/life-threatening, otherwise they are mild to moderate in reaction.

- CNS: Tinnitus, perioral numbness, seizure, coma
- CV: Hypotension, arrhythmia, bradycardia, heart block, cardiac arrest
- EENT: N/A
- ENDO: N/A
- GI: Fecal Incontinence
- GU: Urinary incontinence
- INTEG: N/A
- MS: N/A

### **Nursing Implications:**

- Blood pressure: Hypotension
- Pain: N/A
- Edema: N/A
- I&O (intake & output): N/A
- Allergic reaction: Rare
- Signs and symptoms:

**Drug Name:** Fentanyl

**Other Names:** Sublimaze

**Classification:** Opioid analgesic

**Mode of Action:** Mu receptor agonism

**Storage and Stability:** Requires storage in access controlled container. (Omni cell); No issues with stability at normal temperatures

**Metabolism:** Metabolized by the liver

**Preparation:** Prepared in sterile fashion

**Administration:** Administered intrathecally

**Incompatibilities:**

- Contraindications* – Allergy to fentanyl
- Precautions* – Respiratory Depression

#### **Side Effects:**

Adverse effects indicated in *italics* are the most frequent adverse effects.

Adverse events in **bold** are severe/life-threatening, otherwise they are mild to moderate in reaction.

- CNS: Confusion, loss of consciousness, headache
- CV: Hypotension
- PULM: Respiratory depression, Apnea
- EENT: N/A
- ENDO: N/A
- GI: Constipation, Nausea
- GU: Urinary retention
- INTEG: N/A
- MS: N/A

#### **Nursing Implications:**

- Oxygenation: Apnea
- Blood pressure: Hypotension
- Pain: N/A
- Edema: N/A
- I&O (intake & output): N/A
- Allergic reaction: Rare
- Signs and symptoms:

**Investigational New Drug (IND) Application Required?:** No

**Investigational Device Exemption (IDE) Required?:** No

#### **11.0 STATISTICAL CONSIDERATIONS**

**Demographic Variables:** Age, weight, height, past medical history, procedure type.

**Control Variables:** Group B (10 mg of preservative-free isobaric bupivacaine and 12.5 mcg of fentanyl) vs Group BE (5 mg of preservative-free isobaric bupivacaine and 12.5 mcg of fentanyl with 10 ml of sterile saline through epidural)

**Study Variables:** The primary endpoint is the time until PACU discharge requirements are met. The secondary endpoints are time elapsed to achieve T10 sensory level, degree of peak motor blockade, time elapsed until motor block regresses to modified Bromage score < 2, duration of the spinal block, and patient satisfaction score.

**General Data Analysis:** All demographic and clinical variables with continuous measures will be expressed as means and standard deviations; categorical factors will be expressed as proportions. For non-normal data, the medians and interquartile ranges will be displayed. The distribution of the continuous factors will be examined using the Kolmogorov-Smirnov test. For data that are normally distributed, One-way analysis of variance (ANOVA) will be used to compare the two types of anesthesia. For data that are not normally distributed, the Kruskal-Wallis test will be used for comparisons. Chi-square and Fisher's exact tests will be used to analyze categorical data. For all comparisons, a p-value less than 0.05 will be considered statistically significant.

**Primary Outcome Analysis.** The primary endpoint for this study is the length of time until PACU discharge requirements are met. One-way ANOVA (or the Kruskal-Wallis test, as appropriate) will be used to assess whether PACU length of stay is significantly associated with type of spinal anesthesia. Linear regression will also be used to evaluate the relationship between method of spinal anesthesia and PACU length of stay, while controlling for relevant clinical and demographic variables.

**Secondary Outcome Analysis:** One-way ANOVA will also be used to compare groups on time to achieve T10 sensory level, degree of peak motor blockade, time elapsed until motor block regresses, and patient satisfaction.

**Additional Data Analysis:** N/A

**Statistical Power and Sample Size Estimates:** Approximately 40 subjects (20 per group) are expected to be enrolled in this study. Assuming a standard deviation of 20 minutes for PACU length of stay, a study with this sample size will have approximately 80.7% power to detect a 20 minute difference and approximately 98.9% power to detect a 30 minute difference in PACU length of stay between Group B and Group BE.

**Study Population Availability:** Approximately 3-5 of these procedures are performed per week, which equals about 200 cases per year. About 80% of these cases will be done under spinal anesthesia for a total of 160 per year. Assuming a 50% enrollment rate, it should take 7 to 8 months to complete enrollment.

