Once informed consent is obtained, study participants will be randomized into two different groups: low dose spinal bupivacaine with EVE (BE), and standard-dose spinal bupivacaine (B). Spinal anesthesia will be administered via CSE in routine fashion by a qualified anesthesia provider that is independent of this study. The primary outcome will be total PACU time defined as the time from admission to PACU until the time patient meets PACU discharge criteria (Modified Bromage scale of < 2, blood pressure and heart rate within 20% of baseline, return of baseline oxygenation status as measured by pulse oximetry, alert with baseline mentation, pain well controlled) (Modified Bromage scale: 0-ability to maintain leg lift for prolonged period; 1- ability to lift legs briefly; 2- ability to bend knees; 3- ability to wiggle toes; 4- no movement of lower extremities). Secondary outcomes will be: (1) time until sensory level of T10 achieved, (2) degree of peak motor block after spinal placement (3) time until return of motor function (Modified Bromage score < 2), (4) duration of the block (defined as time from placement until PACU discharge criteria met), (5) quality of the block (as determined by any pain reported during surgery and/or the need to supplement through the epidural) and (6) patient satisfaction (based off of a 0-10 scale). A total of 40 patients will be recruited for the study.

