**Study Hypothesis:** We hypothesize that patients in the EVE group will meet the criteria for PACU discharge significantly quicker than the traditional bupivacaine group while having adequate surgical anesthesia. We also hypothesize that patients in group BE will reach a T10 sensory level quicker, have a lesser degree of peak motor blockade, and will have a faster recovery of motor function.

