## 5.0 INTERPRETATION OF EXPECTED RESULTS

For each CSE performed, multiple factors will be recorded: patient's age, height, weight, time to onset of T10 sensory level, peak sensory level and peak level of motor block (described by modified Bromage scale), patient pain during surgery, need to use epidural catheter, time to return of motor function, and length of PACU stay. Data will be analyzed by our statistician looking for significant differences in outcomes in the BE group compared to the B group.

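### Every secondary comparison may be called significant at 0.05, with no gate, order or exploratory label, although three secondaries carry directional hypotheses

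*Combined protocol and SAP*

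**What the plan says.** Section 11.0 names one primary endpoint, the time until PACU discharge requirements are met. Under General Data Analysis it gives a single decision rule: "For all comparisons, a p-value less than 0.05 will be considered statistically significant". The tests are non-directional: "One-way analysis of variance (ANOVA) will be used to compare the two types of anesthesia", with Kruskal-Wallis for non-normal data.

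The Secondary Outcome Analysis in the same section begins "One-way ANOVA will also be used to compare groups on time to achieve T10 sensory level, degree of peak motor blockade" and goes on to motor regression and satisfaction, which makes four tests. Study Variables lists five secondaries, adding duration of the block. The summary in Section 1.0 lists six, adding quality of the block.

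Section 4.0 (Study Hypothesis) gives three of them a direction: "patients in group BE will reach a T10 sensory level quicker, have a lesser degree of peak motor blockade, and will have a faster recovery". The recovery meant there is that of motor function. Section 5.0 describes the analysis as follows: "Data will be analyzed by our statistician looking for significant differences in outcomes in the BE group compared to the B group".

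No section makes a secondary test depend on the primary result, sets an order, divides alpha or describes the secondaries as exploratory.

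**The concern.** This is a written rule, not silence on multiplicity. It allows the word significant for each secondary taken alone, and three of them match a direction stated in advance. Suppose PACU time does not differ between the groups. The plan would still let the trial report significantly faster motor recovery, or a significantly quicker T10 level, as a prespecified finding in favour of BE. A reader would have no basis in the plan for treating that result as weaker than the primary. With several secondaries, the chance that at least one reaches p < 0.05 by chance is larger than the 5% that applies to any single one. What is at stake is how the secondary results may be worded and relied on.

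**Working it through.** The plan states no error rate for the secondaries as a set, so there is no figure of its own to reproduce.

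**Inputs**
- Per-comparison threshold: 0.05 (Section 11.0, General Data Analysis).
- Test: one-way ANOVA with two groups, which equals a two-sided t-test.
- Sample size: 20 per group (Section 11.0, Statistical Power and Sample Size Estimates).
- Number of secondary tests, k: 3 (Section 4.0), 4 (Secondary Outcome Analysis) or 5 (Study Variables).
- Correlation between outcomes, ρ: not given in the documents. Assumed equal for all pairs and varied from 0 to 0.9.
- Assumed: no true difference on any of the k outcomes counted.

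**Step 1: independent tests.** P(at least one p < 0.05) = 1 − 0.95^k.
- k = 3: 1 − 0.8574 = 14.3%
- k = 4: 1 − 0.8145 = 18.5%
- k = 5: 1 − 0.7738 = 22.6%

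**Step 2: correlated tests.** Write each test statistic as √ρ·G + √(1−ρ)·E, with G a shared and E a separate standard normal variable. Then

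P = 1 − ∫ φ(g) [Φ((1.96 − √ρ g)/√(1−ρ)) − Φ((−1.96 − √ρ g)/√(1−ρ))]^k dg.

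| k | ρ = 0 | ρ = 0.5 | ρ = 0.8 | ρ = 0.9 |
|---|---|---|---|---|
| 3 | 14.3% | 12.5% | 9.8% | 8.4% |
| 4 | 18.5% | 15.6% | 11.4% | 9.4% |
| 5 | 22.6% | 18.3% | 12.7% | 10.2% |

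Simulating the t-tests themselves with 20 per arm gives nearly the same values. At ρ = 0.5, repeated runs gave 12.4 to 12.7% for three tests and 18.3 to 18.6% for five.

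**Step 3: false results favouring BE only.** Each two-sided test has a 2.5% chance of a false result in that direction. For independent tests, 1 − 0.975^k gives 7.3% (k = 3), 9.6% (k = 4) and 11.9% (k = 5). At ρ = 0.5 it is about 6% for three tests and 9% for five. The matching rate for one test is 2.5%.

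**Step 4: fewer true nulls.** If only two of the three hypothesised secondaries are truly null, the two-sided rate is 1 − 0.95² = 9.75% for independent tests and 7.0% at ρ = 0.9. If only one is null, it is 5%.

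**Step 5: what a scheme would achieve.** Suppose the three hypothesised secondaries are tested only after a significant primary, in a fixed order that stops at the first p ≥ 0.05. The chance of any false claim among the four tests is then at most 5%, whichever nulls are true and whatever the correlation. Holm's method after the same gate has the same bound. Its first step uses 0.05/3 = 0.0167, and for three independent nulls 1 − (1 − 0.0167)³ = 4.9%.

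The sixth outcome, quality of the block, is left out of the ranges. It is categorical, and Section 11.0 assigns categorical data to chi-square or Fisher's exact test. With 20 per arm, the true size of Fisher's test is only about 0.2 to 2.5% for assumed event rates of 5 to 30%, so treating it as another t-test would overstate the rate.

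**The case against.** The strongest reply is that the plan breaks no promise. Its 0.05 is a threshold for each comparison, and each valid test does have a 5% error rate. There is one prespecified primary, which the secondary tests do not inflate, and this is a 40-patient, single-site study. All of that stands. A reader might infer that the plan claims 5% control over the whole set and misses it, or that the trial's main conclusion carries an inflated error rate. The documents support neither reading. Nor does Section 4.0 call its secondary hypotheses confirmatory; it only states them.

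The figures are also conditional. They need every counted null to be true, yet halving the dose may well change motor block. If PACU time truly differs, motor recovery probably differs too, because a modified Bromage score below 2 is itself a discharge criterion. Block duration ends when the discharge criteria are met, so it overlaps both the primary and motor recovery. High correlations, and so the lower end of each range, are therefore plausible. The rates also count false results in both directions.

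These points reduce the size without removing the gap. Under the full null the rate stays above 8% even at a correlation of 0.9. Counting only results that favour BE roughly halves both the rate and its single-test comparator. The plan still offers no ground for withholding the word significant from an isolated secondary when the primary fails.

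**Conclusion.** The concern holds as a limit on what may be claimed from the secondaries. If all counted secondary nulls are true, the chance of at least one false significant secondary is about 8 to 14% for three outcomes, 9 to 19% for four and 10 to 23% for five, as the assumed equal correlation goes from 0.9 to 0. No single figure in these ranges should be quoted as the rate, because the documents give no correlations and list the secondaries inconsistently. The textual facts are certain; the size rests on these assumptions. The point is a cheap improvement worth making. It does not undermine the primary test or call for a different sample size.

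**What to change.** Replace the all-comparisons sentence in Section 11.0 with wording such as:

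> The primary endpoint is tested at two-sided 0.05 and the trial's conclusion rests on it. Secondary outcomes are exploratory and are reported as differences with 95% confidence intervals, without claims of significance.

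Keep the planned covariate-adjusted linear regression as a supporting analysis of the primary, so that the new sentence does not demote it. Report quality of the block in the same way, as a difference in proportions, since adequate surgical anesthesia is part of the main hypothesis in Section 4.0. Amend Section 5.0 to match.

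If the sponsor wants confirmatory claims for the three hypothesised secondaries, test them only if the primary is significant. Use either a fixed order that the sponsor sets before data are seen, or Holm's method. The documents give no basis for preferring one order over another.

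The cost is a few sentences, with no added patients, data or procedures and no change to the primary test. The downside is that a secondary with p < 0.05 outside the scheme is reported descriptively. In a fixed order each test reached keeps the full 0.05; Holm starts at 0.0167.

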### 4.0 OBJECTIVE(S) & HYPOTHESIS

**Purpose:** The purpose of this study is to conduct a single site, prospective, randomized study to compare low-dose bupivacaine with fentanyl in combination with EVE to our traditional bupivacaine dose with fentanyl for short obstetric procedures.

**Outline of Therapy:** Patients who are undergoing either placement of cerclage or D&C will be randomized into two groups: 2 ml of preservative-free, isobaric bupivacaine 0.5% (10mg) with 12.5mcg of fentanyl (Group B), or 1 ml of preservative-free isobaric Bupivacaine 0.5% (5mg) with 12.5mcg of fentanyl (Group BE). Group B will serve as our control group. Each group will receive the spinal medications via a CSE technique. The epidural catheter will then be inserted into the epidural space in the B group, whereas a 10 mL bolus of sterile

saline will be injected through the epidural needle into the epidural space before the epidural catheter is threaded in the BE group. All CSEs will be placed by certified anesthesia providers working at UAB's WIC. Also, the epidural catheters that are placed in both groups can be used at any time throughout the procedure if the surgical anesthesia level is believed to be inadequate. Standard demographic data (age, height, and weight) will be collected in addition to data pertaining to primary and secondary endpoints.

**Primary endpoints or outcomes:** The primary outcome will be time until PACU discharge requirements are met (modified bromage scale of < 2, blood pressure and heart rate within 20% of baseline, return of baseline oxygenation status, alert with baseline mentation, pain well controlled).

**Secondary endpoints or outcomes:** Secondary outcomes will be the time elapsed to achieve T10 sensory level to pinprick, degree of peak motor blockade (recorded at the time of consecutive identical dermatomal sensory levels), time elapsed until motor block regresses to modified Bromage score < 2, duration of the block, quality of the block (as determined by any pain reported during surgery and/or the need to supplement through the epidural), and patient satisfaction.

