## 6.0 ELIGIBILITY & EXCLUSION CRITERIA

### **Eligibility criteria:**

1. Any patient 18 or older undergoing D&C or cerclage placement under neuraxial anesthesia.

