## 7.0 RANDOMIZATION/RECRUITMENT PROCEDURES

**Recruitment:** Eligible patients will be identified using the Horizon WIC operating schedule. Once identified, one of the study investigators will screen the patients using the inclusion and exclusion criteria. If patient has no contraindications, the study will be explained and risks and potential benefits will be discussed by one of the study investigators.

**Randomization:** Once the patient is enrolled into the study, they will randomly be assigned into one of the two study groups. Randomization will be performed via random drawing of sealed envelopes which indicate either B or BE. A qualified anesthesia provider independent of the study will perform the spinal procedure and administer the medication in routine fashion.

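### The leading test of PACU time leaves any cerclage v D&C difference in the error term; naming a linear model on group and procedure type as the one primary analysis is a cheap improvement, with a conditional gain

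*Combined protocol and SAP*

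**What the plan says.** Section 11.0, Primary Outcome Analysis, gives the leading analysis, a comparison of the two anesthesia groups: "One-way ANOVA (or the Kruskal-Wallis test, as appropriate) will be used to assess whether PACU length of stay is significantly associated". The next sentence adds a second analysis: "Linear regression will also be used to evaluate the relationship between method of spinal anesthesia and PACU length of stay". Its adjustment is described only in these words: "while controlling for relevant clinical and demographic variables". The covariates are not listed, and neither analysis is labelled primary or supportive.

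The choice between the two leading tests comes from General Data Analysis in the same section, where a Kolmogorov-Smirnov check is followed by the rule "For data that are not normally distributed, the Kruskal-Wallis test will be used for comparisons".

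The Demographic Variables entry reads "Age, weight, height, past medical history, procedure type", so procedure type is a candidate covariate. Section 6.0 admits two procedures: "Any patient 18 or older undergoing D&C or cerclage placement under neuraxial anesthesia". Section 7.0 describes allocation as "Randomization will be performed via random drawing of sealed envelopes which indicate either B or BE" and mentions no stratification.

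**The concern.** Cerclage and D&C patients enter the same comparison. If they recover at different speeds, the unadjusted test treats that predictable variation as noise. Any chance difference in procedure mix between the arms also stays in the estimated treatment difference. Procedure type is known before treatment and has two levels, so one extra model term would deal with both.

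The missing label and covariate list are a smaller matter, but the same sentence of the plan can settle them. It would then be fixed in advance which p-value is confirmatory if the unadjusted and adjusted results differ. What is at stake is precision, not validity.

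**Working it through.** **Inputs from the plan.** 20 per group, SD 20 min and a treatment effect of 20 min (Section 11.0, sample size paragraph); significance at 0.05 (Section 11.0), taken as two-sided because the plan does not say; PACU recovery of about 1 hour (Section 8.0), used only for the skewed case.

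**Assumed, because the documents are silent.** Procedure difference d = 0, 10 or 20 min; procedure mix 50:50 or 25:75.

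**1. The plan's own figure.** For two groups, ANOVA is the t-test. Standard error = 20 × √(2/20) = 6.32 min; noncentrality = 20/6.32 = 3.16; 38 degrees of freedom. Power is 86.9% for 20 min and 99.6% for 30 min. The plan states 80.7% and 98.9%. Those figures are reproduced with 17 per group, a number that the plan does not mention. This is a separate point, in the conservative direction. The comparisons below start from about 87%.

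**2. How much variance procedure type could remove.** I read the SD of 20 as the total SD, the more natural reading of the plan. With proportion p in one procedure, the variance due to procedure is d² × p(1 − p). At 50:50:
- d = 10: 100 × 0.25 = 25; residual SD = √(400 − 25) = 19.36.
- d = 20: 400 × 0.25 = 100; residual SD = √(400 − 100) = 17.32.

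**3. Power of the adjusted model.** Standard error = residual SD × √[(2/20)/(1 − ρ²)] with 37 degrees of freedom, where ρ is the chance correlation between group and procedure type. Averaged over unstratified 20/20 allocation, the noncentral t gives 85.9%, 88.0% and 93.9% at d = 0, 10 and 20. It gives 86.7% at d = 6 and 87.0% at d = 7, so break-even against 86.9% is near 7 min.

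**4. Simulation** (40,000 trials per cell, normal errors, power in %):

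| SD of 20 taken as | Mix | d (min) | Unadjusted | Adjusted | Change |
|---|---|---|---|---|---|
| Total | 50:50 | 0 | 87.0 | 86.0 | −1.0 |
| Total | 50:50 | 10 | 86.9 | 88.0 | +1.1 |
| Total | 50:50 | 20 | 86.4 | 93.7 | +7.3 |
| Total | 25:75 | 0 | 86.8 | 85.8 | −1.0 |
| Total | 25:75 | 10 | 87.3 | 88.0 | +0.7 |
| Total | 25:75 | 20 | 86.8 | 92.0 | +5.2 |
| Within procedure | 50:50 | 0 | 86.9 | 85.9 | −1.0 |
| Within procedure | 50:50 | 10 | 84.8 | 85.9 | +1.1 |
| Within procedure | 50:50 | 20 | 78.7 | 86.0 | +7.3 |

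For total SD 20 and a 50:50 mix, the median 95% CI half-width is about 12.7 min unadjusted, against 12.85, 12.45 and 11.15 min adjusted at d = 0, 10 and 20.

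**5. Validity.** Type I error is 4.9% to 5.2% for both models. The mean unadjusted estimate lies between −20.07 and −19.93 min for a true −20.

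**6. Chance imbalance.** By the hypergeometric distribution, the arms are four or more patients apart on procedure type in 34.3% of trials (20 of 40 in one procedure) or 27.3% (10 of 40). Four apart shifts the unadjusted difference by (4/20) × d: 2 min at d = 10, 4 min at d = 20.

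**7. Skewed times** (log-normal, mean 60, total SD 20, 20,000 trials). Power for ANOVA, Kruskal-Wallis and the adjusted model is 87.0%, 90.5% and 86.1% at d = 0, and 86.6%, 86.5% and 93.5% at d = 20.

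**The case against.** The best defence is that the plan's test is sound and can be identified. It comes first under Primary Outcome Analysis, the regression is introduced with *also*, and the sample size paragraph powers a plain two-group difference. That stands. A reader might infer from the missing label that the plan inflates type I error or biases the result. The documents do not support this: inflation would need a rule that any significant analysis counts, and the plan states none. The leading test, taken alone, holds its level.

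Second, no section says that procedure type predicts PACU time. The documents describe both procedures as short (Section 1.0) and both as needing a T10 level (Section 2). If recovery is alike, adjustment costs a little, and a material gain appears only when the procedure difference is about as large as the treatment effect. That also stands, and is why the gain is given as a range.

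Third, a chance shift of 2 to 4 min is small against a half-width near 12.7 min, and the standard error already allows for it. True. Adjustment removes an avoidable part of that uncertainty; it does not correct an error.

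Fourth, a rank test can do better with skewed times, as step 7 shows when the procedures do not differ. Of the 4.4 points given up there (90.5 − 86.1), 3.5 are already given up by ANOVA (90.5 − 87.0).

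Finally, a reader might infer that procedure type will not be recorded, since Section 4.0 says "Standard demographic data (age, height, and weight) will be collected in addition to data pertaining to primary and secondary endpoints" and the lists in Sections 5.0 and 8.0 do not name it. That goes too far. Section 11.0 lists it, eligibility depends on it, and the Section 8.0 list also leaves out age, height and weight. The data sheet is not among the documents.

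**Conclusion.** The point holds as a minor, cheap improvement. The planned leading test is valid and unbiased but makes no use of a pre-treatment variable that the plan already lists and does not stratify on. Under the plan's 20 per group, total SD 20 min and 20-min effect, with an assumed 50:50 mix, fixing a model on group and procedure type changes power by about −1, +1 and +7 points at procedure differences of 0, 10 and 20 min. Whether the trial gains depends on a procedure effect that the documents do not give. Even at the unfavourable end, power stays near 86%, above the stated 80.7%.

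**What to change.** 1. In Section 11.0, replace the Primary Outcome Analysis text with wording such as: *The primary analysis is a linear model of PACU time in minutes with terms for group and procedure type (cerclage or D&C). The adjusted difference, BE minus B, is reported with its 95% CI and a two-sided p-value at 0.05. The unadjusted ANOVA or Kruskal-Wallis test, and a regression on group, procedure type, age, height and weight, are supportive.* Past medical history is left out of the wider regression because it is not one defined variable; it can be added if specific conditions are named in advance.
2. In General Data Analysis, after the Kruskal-Wallis rule, add: *This rule does not select the primary analysis of PACU time, which is fixed below.*
3. Check that procedure type is on the data sheet, and add the field if it is not.

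The cost is this wording and at most one data-sheet field. No patients or visits are added, and the target remains a difference in minutes. The statistical price is one degree of freedom, about 1 point of power if procedure type is not prognostic, and the loss against a rank test in the skewed case with no procedure effect. The change should be made before outcome data are examined by group.

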Another advantage of the CSE technique is the ability to treat inadequate surgical anesthesia during surgery. If a spinal technique is performed, no additional medication can be given in the neuraxial space due to the fact it is just a one-time shot. With a CSE, an epidural catheter is placed in the epidural space after the spinal block is performed. This allows the provider to administer LA medication through the epidural catheter to maintain an adequate surgical block throughout the procedure. Therefore, if the spinal block begins to regress and the patient experiences any pain, LA can be administered through the epidural catheter to re-establish an adequate surgical block.

The ability to administer less bupivacaine will allow for a shorter duration of anesthesia and a quicker return to baseline function. Although we would like to reduce PACU times, we also understand the importance of providing an adequate surgical block. There is evidence that supports adequate surgical levels with low dose bupivacaine. One study has shown that equipotent doses of 10mg of bupivacaine with high opioid administration can produce up to T2 level

analgesia when combined with EVE. In this study, there was not only a significant difference in maximum block achieved, but also in time to onset of block. Yet another study demonstrated adequate analgesia for cesarean section when combining doses as low as 5mg of bupivacaine with EVE. Given that only a T10 level would be required for cerclage or D&C, it is reasonable to believe that low doses of bupivacaine combined with EVE would provide an adequate surgical block while reducing the time needed to recover from the spinal block.

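### Section 11.0 omits block quality from its secondary endpoints, leaves adequacy to a p<0.05 rule, and has no rule for patients who never reach T10

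*Combined protocol and SAP*

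**What the plan says.** Section 4.0 (Study Hypothesis) expects BE patients to "meet the criteria for PACU discharge significantly quicker than the traditional bupivacaine group while having adequate surgical anesthesia". It adds that "patients in group BE will reach a T10 sensory level quicker".

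Section 4.0 (Secondary endpoints) includes "quality of the block (as determined by any pain reported during surgery and/or the need to supplement through the epidural", and Section 1.0 lists the same endpoint. Section 8.0 (Measured end-points, items f and g) collects the two components. Of the epidural catheters, Section 4.0 (Outline of Therapy) says that they "can be used at any time throughout the procedure if the surgical anesthesia level is believed to be inadequate".

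Section 11.0 (Study Variables) then gives five secondary endpoints: time to T10, peak motor block, motor regression, block duration and satisfaction. Block quality is not among them. The Secondary Outcome Analysis reads "One-way ANOVA will also be used to compare groups on time to achieve T10 sensory level, degree of peak motor blockade" and goes on to motor regression and satisfaction. General Data Analysis reports categorical factors as proportions, allows chi-square and Fisher's exact tests, applies Kruskal-Wallis to non-normal data, and sets p<0.05 for all comparisons. Section 5.0 states: "Data will be analyzed by our statistician looking for significant differences in outcomes in the BE group compared to the B group".

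Section 2 sets the level that matters: "Given that only a T10 level would be required for cerclage or D&C". No section says how a patient who does not reach T10, or reaches it only after local anaesthetic through the catheter, enters the time-to-T10 comparison.

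**The concern.** BE receives half the spinal dose of B, so a shorter PACU stay supports the hypothesis only if the block was good enough for surgery. The endpoint that speaks most directly to this drops out of the statistical section. What remains by default is a test for a difference, and failing to find a difference is not evidence of adequacy.

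The T10 gap is a different problem. ANOVA needs a number for every patient it includes. Someone whose block stops short of T10 has none, and the easy course is to leave her out. That removes the worst blocks from the comparison. If more of them are in BE, the remaining BE patients look faster, which is the direction the protocol hypothesises.

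**Working it through.** The plan states no figure for block failure or T10 attainment, so there is none to reproduce. Its power figures concern PACU stay only.

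**Inputs.** 20 per group (Section 11.0, sample size). Significance at p<0.05 (Section 11.0), taken as two-sided because sidedness is not stated. Failure counts, failure rates and T10 distributions are assumptions.

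**Block failure: what p<0.05 can show**

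1. Fisher's exact test, 4/20 (BE) v 0/20 (B). The probability that all four failures fall in BE is C(20,4)/C(40,4) = 4845/91390 = 0.053. Doubling for the mirror-image table gives p = 0.106. Significance against zero failures in B needs at least 5 in BE: 2 × 15504/658008 = 0.047.
2. Newcombe 95% interval for BE minus B, built from the Wilson limits (l, u) of each proportion p. Upper limit = d + √[(u_BE − p_BE)² + (p_B − l_B)²].
   - 4 v 0: Wilson upper limit for 4/20 is 0.416. Upper = 0.20 + √[(0.416 − 0.20)² + 0²] = 0.416, so the interval is −0.1 to +41.6 points.
   - 1 v 1: Wilson limits for 1/20 are 0.0089 and 0.2361. Upper = 0 + √[(0.1861)² + (0.0411)²] = 0.191, or +19.1 points.
   - 2 v 1: Wilson upper limit for 2/20 is 0.3010. Upper = 0.05 + √[(0.2010)² + (0.0411)²] = 0.255, or +25.5 points.
3. With 0/20 failures in BE, the Clopper-Pearson two-sided 95% upper limit is 16.8%.
4. Exact power of Fisher's test, assuming 5% failure in B:

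| Assumed failure in BE | Power |
|---|---|
| 15% | 7% |
| 20% | 17% |
| 30% | 45% |

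A non-significant result would therefore be likely even with a substantial excess of failed blocks.

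**Time to T10: effect of dropping non-attainers**

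Underlying times were simulated as log-normal with median 8 min and log-SD 0.3, 0.5 or 0.7, identical in both arms, 20 per arm, 20,000 runs per setting (all assumed). A patient beyond her arm's cut-off never reaches T10 and is dropped. ANOVA is run on the rest. The table gives the rate of p<0.05 with BE faster; the nominal rate is 2.5%.

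| Non-attainment, BE v B | False 'BE faster' |
|---|---|
| Same cut-off in both arms (5%, 10% or 20%) | 2.3-2.8% |
| 10% v 0% | 9-10% |
| 20% v 5% | 15-17% |

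Three checks on how far this reaches, using fixed numbers of patients dropped:
- If the loss is in B only (slowest 2 of 20), the rate falls to 0.6-0.7%, so the bias reverses.
- If 4 of 20 BE patients are lost at random with respect to speed, there is no inflation (1.9-2.5%).
- Kruskal-Wallis on the attained times does not cure the problem. With the slowest 2 of 20 dropped from BE only, it gives about 8%, against 11% for ANOVA. With non-attainers kept and ranked tied slowest, the rate did not exceed 2.4% when at least as many were in BE as in B.

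**The case against.** **Block quality already has an analysis.** It is categorical, and Sections 5.0 and 11.0 together imply proportions by arm and a chi-square or Fisher test. The Secondary Outcome Analysis sentence is not exhaustive either: block duration is a listed endpoint that it also omits. This stands. A reader might infer that half of the hypothesis has no analysis at all, and the documents do not support that. The gap is narrower: the endpoint is not listed, it is not said whether pain and supplementation are combined, and there is no criterion for adequacy.

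**The plan never says it will read p>0.05 as adequacy.** True, and it should not be accused of that. But significance is the only rule it offers, and no section says how adequacy will be judged.

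**Block quality is not expressly tied to adequacy.** Also true; the link is a fair inference from the endpoint's definition. Sections 5.0 and 8.0 also record "peak sensory level and peak level of motor block" or its equivalent, but peak sensory level is not a named endpoint. Reading T10 attainment as part of adequacy makes a rule for non-attainers more necessary.

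**The T10 bias is conditional.** This stands. A reader might infer that dropping non-attainers always inflates error. With the same attainment cut-off in both arms it does not. Inflation needs genuinely worse attainment in BE. The documents give no rate, and Section 2 argues that the low dose with volume extension should suffice.

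**The remedy does not narrow the intervals.** Correct: 20 per group is unchanged. What changes is that the imprecision is reported.

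**Conclusion.** Both omissions are in the text, and both should be fixed before the data are analysed. For block quality, the default significance rule cannot support an adequacy claim at 20 per group: even one failure in each arm leaves an excess in BE of up to 19.1 points, and four against none would pass as non-significant. These intervals follow from the sample size and illustrative counts.

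For time to T10, the endpoint is undefined for non-attainers. Dropping them raises the false 'BE faster' rate to roughly 9-17% in the two unequal-attainment scenarios examined. That size rests on assumed log-normal times, loss of the slowest patients, and worse attainment in BE. The omission is certain; how often it would matter is unknown.

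A reader might carry this over to PACU time. Nothing here shows bias in the primary outcome; only one secondary endpoint is exposed to the T10 problem.

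**What to change.** In Section 11.0:

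1. **Block failure.** List it as a secondary endpoint, defined as pain during surgery or epidural supplementation. Report counts by arm and the BE-minus-B risk difference with a 95% CI. Use Fisher's exact test for any p-value, because expected counts are small. Word any statement on adequacy from the interval, not from p>0.05, and acknowledge its width.
2. **Time to T10.** Compare all randomised patients by a rank test. Rank as slowest those who do not reach T10, or reach it only after an epidural top-up, and report their number by arm. The assigned saline bolus in BE is part of the intervention and does not count as a top-up. A time-to-event analysis, or separate reporting of attainment, are alternatives; what matters is that one rule is fixed in advance.
3. **Optional.** Name Kruskal-Wallis for peak motor score and satisfaction. The general rule for non-normal data largely covers these.

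The cost is a few sentences and possibly one data field. Section 8.0 already records drugs administered, but the data sheet is not in the documents, so it should be checked that the top-up time is captured. Sample size and primary analysis are unchanged. The price is a more cautious adequacy statement.
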